2.1.3 Exploratory Objectives

The exploratory objectives are to:

- Assess changes in biomarkers of potential harm (BOPHs) and biomarkers of exposure (BOEs) (same as in the primary objective) from Baseline through Week 24 (EOS) between the subgroups that used different flavored Test e-vapor products.
- Assess changes in urine nicotine equivalents (NE) from Baseline through Week 24 (EOS) within and between Test and Control groups.
- Assess changes in the QGEN and TQOLIT questionnaires and the Cough Questionnaire responses from Baseline through Week 24 (EOS) between the Test and Control groups.
- Assess reasons for test product use/not-use at EOS and modified Cigarette Evaluation Questionnaire (mCEQ) questionnaires from Baseline to Week 24 (EOS) for the Test groups.
- Collect blood and urine samples for future assessment of BOE and or BOPH.

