6.2.6 Questionnaires

The responses and the following factor scores from the QGEN and TQOLIT will be presented and listed by subject and study visit:

- QGEN Physical Health General Score
- QGEN Emotional Health General Score
- QGEN estimated Physical Component Summary
- QGEN estimated Mental Component Summary
- TQOLIT Physical Functioning Supplemental
- TQOLIT General Health-Confidence
- TQOLIT Smoking Symptoms
- TQOLIT Smoking or Vaping Impact

The mCEQ will be considered as a 7-point scale and treated as a continuous variable. The responses from mCEQ-C or mCEQ-E will be listed as individual responses and as following factor scores¹ by subject and study visit:

- Smoking satisfaction: average of the response scores from questions 1, 2, and 12;
- Psychological reward: average of the response scores from questions 4 to 8;
- Aversion: average of the response scores from questions 9 and 10;
- Enjoyment of sensation: response score from question 3;
- Craving Reduction: response score from question 11.

Descriptive statistics (n, n missing, mean, SD, CV%, SEM, minimum, Q1, median, Q3, maximum, and 95% CI) of each of the response score and factor score will be provided by study group and study visit.

The responses from Cough Questionnaire (Baseline*, Visits 3 and 5) and Reasons of Use/Not-Use Test Product Questionnaire (Visit 5) will be listed by subject and study

¹ Cappelleri et al. 2007. Confirmatory factor analysis and reliability of the modified cigarette evaluation questionnaire. Addictive Behaviors. (32)912-923

visit. The frequency (n, %) of responses to Questions I and III through X will be summarized by study group. The responses to Question II will be summarized by study group using the same descriptive statistics as for the above questionnaires.

The above questionnaire analyses will be conducted using the dataset of subjects with a baseline and at least one post-baseline response for each individual question, with the exception of Reasons of Use/Not-Use, which will be summarized using available data.

*Baseline values reported on Day 1 (Week 1) of the 12-week ALCS-RA-16-06-EV study (CA20130) will be used.

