6.3.3 Exploratory Endpoint Analysis

The same statistical analysis model defined in the primary analysis Section 6.3.2 will also be used for the exploratory analysis to provide estimates for:

- Absolute changes in urine nicotine equivalents (NE) from Baseline to Week 18 and Week 24 between the each Test Group and the Control group and between the combined e-vapor use group (Test 1 + Test 2) and the Control group (mITT population).

For the following endpoints, the same statistical analysis model defined in the primary analysis Section 6.3.2 but without the fixed effect of BMI will be used for the exploratory analysis to evaluate:

- absolute changes in the QGEN and TQOLIT questionnaire responses from Baseline to Week 18 and Week 24 between the each Test Group and the Control group.

The following SAS codes will be used to perform the analysis:

```
Proc mixed data=<>;
Class subject gender group visit age;
Model response = gender group visit group*visit age baseline/ddfm=kr;
Repeated visit/type=<type> subject=subject;
LSmeans group*visit/CL alpha=0.05 pdiff;
Run;
```

For the endpoints with only Baseline and Week 24 measurements, an ANCOVA model will be used for the exploratory analysis to evaluate:

- absolute changes in the mCEQ factor score from Baseline to Week 24 in the Test and Control groups.

In the model, study group, gender, and age class (less than 45 years or greater or equal to 45 years) are the fixed effect factors. The baseline [Day 1 (Week 1) of the 12-week ALCS-RA-16-06-EV study (CA20130)] value of the measurement is the fixed effect covariate.

The following SAS codes will be used to perform the analysis:

```
proc mixed data=<>;
class subject gender group age;
model testname = gender group age baseline;
lsmeans group/diff cl alpha=0.05;
run;
```

Responses to the Reasons of Use/Not-Use Test Product questionnaire will be summarized using frequency count tables for each question.

Questionnaire analyses will be conducted using the dataset of subjects with a baseline and at least one post-baseline response for each individual question.

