| Question | Response | --- Baseline --- | | --- Visit 3 --- | | --- Visit 5 ----- | |
|---|---------------------|------------------|--------|-----------------|--------|-------------------|--------|
| | | Test 1 | Test 2 | Test 1 | Test 2 | Test 1 | Test 2 |
| | | n | (%) | n | (%) | n | (%) |
| I. Did you have a cough in the past 30 days? | | | | | | | |
| | Yes | XX | (XX) | XX | (XX) | XX | (XX) |
| | No | XX | (XX) | XX | (XX) | XX | (XX) |
| III. When does the cough occur? (choose one) | | | | | | | |
| | Middle of the Night | XX | (XX) | XX | (XX) | XX | (XX) |
| | Daytime | XX | (XX) | XX | (XX) | XX | (XX) |
| | Anytime | XX | (XX) | XX | (XX) | XX | (XX) |
| IV. Do you have a cough that comes mainly from your chest and not your throat? | | | | | | | |
| | Yes | XX | (XX) | XX | (XX) | XX | (XX) |
| | No | XX | (XX) | XX | (XX) | XX | (XX) |
| V. Do you ever cough up phlegm? | | | | | | | |
| | Never | XX | (XX) | XX | (XX) | XX | (XX) |
| | Seldom | XX | (XX) | XX | (XX) | XX | (XX) |
| | Sometimes | XX | (XX) | XX | (XX) | XX | (XX) |
| | Often | XX | (XX) | XX | (XX) | XX | (XX) |
| | Always | XX | (XX) | XX | (XX) | XX | (XX) |

<similar for remaining questions (VI, VII, VIII, IX, X) and responses>

Note: Baseline = Day 1 (week 1) of the 12-week ALCS-RA-16-06-EV study (CA20130)
 Visit 3 = Week 18 (Day 126 ± 3)
 Visit 5 = Week 24 (Day 168 ± 3)

Test 1 Group = e-Vapor Product XLCB

Test 2 Group = e-Vapor Product XLMB

Control Group = Continue smoking lit-end conventional cigarette

Program: /CAXXXX/ECR/sas_prg/pksas/PROGRAMNAME.sas DDMMYYYY HH:MM

Programmer note: A third column labelled “Control” will be added to each Visit.

Table 14.2.4.4.2 Summary of Cough Questionnaire Question II by Study Group and Visit

| Question | Visit | Statistic | Group | | |
|--|----------|-----------|--------|--------|---------|
| | | | Test 1 | Test 2 | Control |
| II. How long have you had the cough? (Days) | Baseline | n | XX | XX | XX |
| | | n missing | X | X | X |
| | | Mean | XX | XX | XX |
| | | SD | XX | XX | XX |
| | | CV% | XX | XX | XX |
| | | SEM | XX | XX | XX |
| | | Minimum | XX | XX | XX |
| | | Q1 | XX | XX | XX |
| | | Median | XX | XX | XX |
| | | Q3 | XX | XX | XX |
| | | Maximum | XX | XX | XX |
| | | 95% CI | X, X | X, X | X, X |

<Data will be presented similarly for Visits 3 and 5)

Note: Baseline = Day 1 (week 1) of the 12-week ALCS-RA-16-06-EV study (CA20130)
Visit 3 = Week 18 (Day 126 ± 3)
Visit 5 = Week 24 (Day 168 ± 3)

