Appendix 16.2.6.12.4.1 Cough Questionnaire

- I. Did you have a cough in the past 30 days? (1 = Yes, 2 = No)
- II. How long have you had the cough?
- III. When does the cough occur? (1 = Middle of the night, 2 = Daytime, 3 = Anytime)
- IV. Do you have a cough that comes mainly from your chest and NOT from your throat (1 = Yes, 2 = No)
- V. Do you cough up phlegm? (1 = never, 2 = seldom, 3 = Sometimes, 4 = Often, 5 = Always)
- VI. Do you cough more than the average person? (1 = Yes, 2 = No)
- VII. Have you taken medications for your cough? (1 = Yes, 2 = No)
- VIII. Have you sought the help of a health care provider to treat your cough? (1 = Yes, 2 = No)
- IX. In the last 24-hours, has your cough disturbed your sleep? (1 = All of the time, 2 = Most of the time, 3 = A good bit of the time, 4 = Some of the time, 5 = A little of the time, 6 = Hardly any of the time, 7 = None of the time)
- X. In the last 24-hours, how many times have you had coughing bouts? (1 = All the time, 2 = Most times during the day, 3 = Several times during the day, 4 = Some times during the day, 5 = Occasionally through the day, 6 = Rarely, 7 = none)

Program: /CAXXXX/ECR/sas_prg/stsas/lis_PROGRAMNAME.sas DDMMYYYY HH:MM

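### The question-by-question dataset rule limits Cough Questions II and III to subjects who cough at Baseline and again at Visit 3 or 5 (minor, exploratory)

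*SAP*

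**What the plan says.** The exploratory objectives (SAP Section 2.1.3) include assessing changes in "the Cough Questionnaire responses from Baseline through Week 24 (EOS) between the Test and Control groups". Section 2.2 names the responses at Baseline, Week 18 and Week 24 as the outcome, and Section 6.1.5.2 lists the responses to each question.

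Section 6.2.6 plans frequencies for Questions I and III to X and continuous descriptive statistics for Question II. It then restricts the questionnaire analyses to a dataset defined one question at a time: they are "conducted using the dataset of subjects with a baseline and at least one post-baseline response for each individual question". The only exemption is worded "with the exception of Reasons of Use/Not-Use, which will be summarized using available data". Section 6.3.3 states the restriction again, with no exemption for cough: "Questionnaire analyses will be conducted using the dataset of subjects with a baseline and at least one post-baseline response for each individual question".

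Appendix 16.2.6.12.4.1 gives the items:

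- Question I: "I. Did you have a cough in the past 30 days? (1 = Yes, 2 = No".
- Question III: "III. When does the cough occur? (1 = Middle of the night, 2 = Daytime, 3 = Anytime".
- Question II asks how long the cough has lasted. The shell of Table 14.2.4.4.2 summarises it in days, under the row label "II. How long have you had the cough? (Days".

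The SAP states no skip pattern, no code and no denominator for a subject without a cough on Questions II and III.

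**The concern.** A rule requiring a baseline and a later response is harmless for a scale that everyone can answer at every visit. It behaves differently for an item that can be answered only by someone with the symptom. There, having a response is itself an outcome, so requiring one at Baseline and another afterwards selects subjects on what happened to their cough after product assignment.

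Two things follow for Questions II and III. Answers that were actually recorded are thrown away, for example the duration and timing of a cough that began during the study. And the Baseline columns no longer describe the coughs present at Baseline, only those that were seen again later. If cough resolves at different rates in the Test and Control groups, the Baseline columns are selected differently by group, so the groups are not compared like with like on these two items.

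**Working it through.** There is no planned figure to reproduce: the SAP gives no cough prevalence, resolution or onset rate, and no sample size or test for cough. The check is to apply the stated rule to the response codes.

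**Step 1: which items depend on a cough.** Question I is Yes/No and can be answered by everyone. Questions II and III have no answer for a subject without a cough. Questions IV, VI, VII and VIII have a No; V has a never code; IX and X each have a code for none. Only II and III depend on a cough by their own coding.

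**Step 2: the rule applied to Questions II and III.** Assume that a subject without a cough leaves both blank, and that no visit is missed.

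| Baseline | Visit 3 | Visit 5 | Result for II and III |
|---|---|---|---|
| cough | cough | cough | kept |
| cough | cough | none | kept, Visit 5 blank |
| cough | none | cough | kept, Visit 3 blank |
| cough | none | none | dropped, Baseline answer lost |
| none | cough | cough | dropped, two answers lost |
| none | cough | none | dropped, one answer lost |
| none | none | cough | dropped, one answer lost |
| none | none | none | nothing to summarise |

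Of the seven patterns with a cough at some visit, three are kept and four are dropped. One post-baseline response is enough, so a cough that is present at Visit 3 and gone by Visit 5 does not remove the subject.

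**Step 3: how many subjects.** Let n be the group size, p the proportion with cough at Baseline, r the proportion of those whose cough is gone at both later visits, and q the proportion of the rest who develop a cough.

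- Kept: n × p × (1 − r)
- Dropped: n × p × r + n × (1 − p) × q
- Share of ever-coughers dropped: [p × r + (1 − p) × q] / [p + (1 − p) × q]

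The SAP supplies none of p, r or q. With q assumed at 10%, the share runs from (0.06 + 0.04) / (0.60 + 0.04) = 16% at p = 60%, r = 10%, to (0.14 + 0.08) / (0.20 + 0.08) = 79% at p = 20%, r = 70%. That range shows only that the share is undetermined; it is not an estimate.

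**Step 4: Question II over time.** The table shells place Visit 3 at Week 18 (Day 126 ± 3) and Visit 5 at Week 24 (Day 168 ± 3). A cough that continues unchanged lengthens by elapsed time alone: 18 × 7 = 126 days and 24 × 7 = 168 days, approximately. A rising mean in Table 14.2.4.4.2 therefore does not by itself show worsening.

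**Step 5: Question I.** Everyone attending can answer it, so the rule removes nobody on account of cough status. Table 14.2.4.4.1 shows its frequencies at Baseline, Visit 3 and Visit 5, and the programmer note adds the Control column.

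**The case against.** The strongest reply is that the objective is still served. Question I measures the presence of cough, keeps all subjects with data, and is tabulated by group and visit. No model or test is planned for cough, the endpoint is exploratory, Section 6.1.5.2 defines no change score for it, and every response is listed by subject and visit. All of this stands, and it is why the point is minor.

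Three stronger readings are tempting, and the document does not support them.

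- A reader might infer that the rule removes the very change the objective asks about. It does not: a fall or rise in cough prevalence remains visible through Question I.
- A reader might extend the loss to Questions IV to X, since several refer to the subject's cough. All have a negative code, and loss would arise only if the form skips them after a No to Question I, which the SAP does not say.
- A reader might infer that Question II would point in the wrong direction, with the improving group showing the longer cough. That needs assumed cough durations and resolution rates that the SAP does not give. Elapsed time adds the same number of days to an unchanged cough in either group, and whether any gap appears depends on which coughs are assumed to resolve in which group.

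The reply does not rescue the rule for II and III. Followed as written, it still discards recorded answers and selects the Baseline columns on later outcome. Question I frequencies at separate visits also cannot tell resolved coughs from new ones.

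**Conclusion.** The point holds in a limited form. For Questions II and III, and only those, the rule in Sections 6.2.6 and 6.3.3 restricts the summary to coughs present at Baseline and at one or more later visits. Conclusions about whether subjects cough are not affected. The number of subjects lost cannot be stated from the SAP.

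The conclusion rests on two assumptions: that subjects without a cough leave II and III blank, which is the natural reading of items with no such code, and that the rule works separately for each question, which is how it is worded. It is a minor defect in two exploratory, descriptive items, worth correcting because the correction is cheap.

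**What to change.** 1. In Sections 6.2.6 and 6.3.3, exempt Cough Questions II and III from the question-by-question rule. Summarise them at each visit on available data among subjects answering Yes to Question I at that visit, and show that number against all Question I respondents. For Question III, a no-cough category is an acceptable alternative.
2. In Table 14.2.4.4.2, label Question II as describing coughs present at that visit, and note that the duration of an unchanged cough rises by about 126 days by Week 18 and 168 days by Week 24.
3. Add one shift table for Question I from Baseline to Visit 5 (resolved, persistent, new, never) by study group.

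The SAP already uses available data for the Reasons of Use/Not-Use questionnaire, so the approach is consistent with its own practice. The cost is a few sentences and one table, with no new data. The downside is that different subjects contribute to II and III at different visits, so those columns must not be read as within-subject change.

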6.3 Statistical Analyses

6.3.1 Primary Endpoint Analysis

A linear mixed model for repeated measures (MMRM) analysis will be used for comparing each test group (Test 1 or 2) to the control group in the mean absolute change from Baseline to Week 24 (Visit 5) in each primary biomarker (WBCs, HDL-C, 8-epi-prostaglandin F_{2α}, 11-dehydrothromboxane B₂, sICAM-1, total NNAL, and COHb). In the model, study group (each of the two test group vs control), visit, and study group by visit interaction, gender, age class (less than 45 years or greater or equal to 45 years), and BMI class (less than 25 kg/m² or greater or equal to 25 kg/m²) are the fixed effect factors. The baseline value of the response biomarker, where baseline is defined as the value reported on Day 1 (Week 1) of the 12-week ALCS-RA-16-06-EV study (CA20130), is the fixed effect covariate and subject is the random effect factor. A restricted maximum likelihood estimation method will be applied and several covariance structures will be tried. Five candidate covariance structures will be considered: compound symmetry, first order autoregressive, first order autoregressive with a random subject effect, unstructured and Toeplitz. The most appropriate covariance structure will be determined based on the AIC criteria (the covariance structure with the smallest AIC will be chosen). If the model cannot be converged, a robust sandwich estimator for the standard error of the fixed effects will be used. The least-square mean difference, 95% confidence interval and p-value will be provided for the group difference. Pairwise comparisons (Test 1 vs. control, and Test 2 vs. control) will be performed using a Dunnett's test at a 2-sided significance level of 0.05 to adjust for multiplicity. The analysis will be conducted on the mITT and PP datasets.

The following SAS codes will be used to perform the analysis.

```
Proc mixed data=<>;
Class subject gender group visit age bmi;
Model response = gender group visit group*visit age bmi baseline/ddfm=kr;
Repeated visit/type=<type> subject=subject;
LSmeans group*visit/CL alpha=0.05 pdiff dunnett('CONTROL');
Run;
```

Note: This model will include both the Week 24 value (primary endpoint) and Week 18 value (secondary endpoint). The above analysis will also output the residual diagnosis to check for normality and to identify outliers).

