2.2 Outcome Variables

Primary

The primary outcome variables are the absolute change from Baseline* Week 1 (Day 1) to Week 24 for each of the following primary biomarkers:

- whole blood WBC Count
- serum HDL-C
- creatinine-adjusted urine 8-epi-prostaglandin F_{2α}
- creatinine-adjusted urine 11-Dehydrothromboxane B₂
- serum sICAM1
- creatinine-adjusted urine total NNAL
- blood COHb saturation

*Baseline of the 12-week ALCS-RA-16-06-EV study (CA20130), Week 1, will be used.

Secondary

The secondary outcome variables are:

- Changes in FEV₁, FVC, and FEV₁/FVC ratios from Baseline to Week 18 and to Week 24 (EOS) in the Test and Control groups.
- The absolute change from Baseline to Week 18 for each of the primary biomarkers for each study group.
- The absolute change from Baseline to Week 24 for each of the primary biomarkers in the combined e-vapor use group (Test 1 + Test 2).
- Number of cigarettes smoked per day and test product used per day (number of new cartridges used and number of puffs taken, either ≤ 20 puffs or > 20 puffs) during Week 12 through week 24
- Frequency and percentage of subjects with a reduction, no change, or increase in cigarettes used per day from Baseline to Week 24
- Frequency and percentage of subjects with a reduction, no change, or increase in e-vapor cartridges used per day from Baseline to Week 24
- Creatine-adjusted urine NNN determined at Baseline, Week 18, and Week 24
- eCO determined at Baseline, Week 15, Week 18, Week 21, and Week 24

Exploratory

The exploratory outcome variables are:

- The differences between Baseline and Week 24 for the primary biomarkers in the Test groups.
- The creatinine-adjusted urine nicotine equivalent (NE) determined at Baseline, Week 18, and Week 24
- The absolute change in creatinine-adjusted urine NE from Baseline to Week 18 and from Baseline to Week 24
- Responses (Score) to the QGEN and TQOLIT questionnaires and the Cough Questionnaire recorded at Baseline, Week 18, and Week 24
- Responses to Reasons for Use and Not-use of Test Product at Week 24 (Test groups only) and mCEQ questionnaires from Baseline to Week 24

Clinical Safety

- AEs and SAEs
- Blood pressure, ECG, vital signs, clinical chemistry, urinalysis, and hematology

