3. STUDY DESIGN

This research study is an extension of the 12-week ALCS-RA-16-06-EV study (CA20130). A total of up to 250 subjects (up to 100 in each of the Test groups and 50 in the Control group) who were compliant with the requirements of the 12 week ALCS-RA-16-06-EV study and continued to satisfy all inclusion/exclusion criteria of that study were planned to be enrolled. The sample size of the extension study is much smaller and the statistical analysis is mostly exploratory in nature.

The study utilized a parallel-group, open-label, controlled design and was conducted at multiple study sites. A total of 150 adult male and female (neither gender should account for more than 60% of the population) smokers (30 to 65 years of age, inclusive, determined at Screening [Visit 1] of the 12-week ALCS-RA-16-06-EV study) who completed the 12-week ALCS-RA-16-06-EV study (CA20130), were compliant with the requirements of the 12-week study, and continued to satisfy all inclusion/exclusion criteria of that study, were invited to enroll into this study and remain in the group into which they were randomized in the 12-week ALCS-RA-16-06-EV study.

- Control Group (n=52): Continue smoking under ad libitum use of subjects' own brand of conventional lit-end cigarettes, without use of any other type of tobacco/nicotine containing product, for the entire additional 12 weeks.

- Test 1 Group (n=50): Continue ad libitum use of test e-vapor products (Product XLCB), without use of any other type of tobacco/nicotine containing product, for the entire additional 12 weeks.
- Test 2 Group (n=48): Continue ad libitum use of test e-vapor products (Product XLMB), without use of any other type of tobacco/nicotine containing product, for the entire additional 12 weeks.

Subjects in the Test groups will be provided a 3-week supply of the test product to which they were randomized in the 12-week ALCS-RA-16-06-EV study and will be given a return date for Visit 2 (Week 15).

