4. ANALYSIS POPULATIONS

The Clinical Safety Population (CSP):

The CSP will consist of all subjects who are enrolled into this study and record at least one use of study products (i.e., conventional cigarettes or test e-vapor products) after Week 12.

The Modified Intent-to-Treat (mITT) Population:

The mITT population includes those subjects in the CSP population for which there is a baseline for a primary biomarker and at least one post-baseline biomarker measure for the primary biomarker after Week 12.

The Per-Protocol (PP) Population:

The PP population will be a subset of the mITT Population, which is comprised of subjects who completed the study without any major protocol violations, which are defined as:

- Control group: subjects who quit cigarette smoking (either by self report or NNN criteria of $\geq 80\%$ reduction in NNN from baseline at Visit 3 or 5).
- Test groups: subjects who self-report use of $> 10\%$ of baseline CPD over the course of the study*, subjects with an eCO > 8 ppm at any one visit in Visits 2 - 5, or subjects whose NNN levels are consistent with smoking cigarettes (ie, $< 80\%$ reduction in NNN from baseline) at Visit 3 or 5, and subjects who used ≤ 2 cartridges per week during any given week from Weeks 13 to 24.

*Baseline is defined as the CPD reported at Screening (Visit 2) of the 12-week ALCS-RA-16-06-EV study (CA20130), and the course of the study (post baseline) is defined as the average number of cigarettes smoked from Day 1, Week 1 of ALCS-RA-16-06-EV through the end of Week 24.

The CSP and PP populations will be used for the analyses of subject demographics, baseline characteristics and tobacco product use.

The mITT and PP populations will be used for the analyses of the primary endpoint. All other endpoints (excluding demographics, baseline characteristics, and safety data) will be analyzed based on the mITT population concept defined for each endpoint that includes subjects who has a baseline value and at least one post-baseline value. A PP population will be applied to the spirometry dataset using the criteria listed above.

The CSP will be used for the analyses of AEs, vital signs, clinical laboratory findings and other study safety related variables.

If it is determined that a subject was pregnant during the study, all of the pregnant subject's safety and biomarker data will be reported, but will be excluded from the biomarker summarization and statistical analyses.

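### The seven primary biomarkers are each tested at 0.05 with no control of error across them, and neither mITT nor PP is named as the set that decides

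*SAP*

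**What the plan says.** - Section 2.2: "The primary outcome variables are the absolute change from Baseline* Week 1 (Day 1) to Week 24 for each of the following primary biomarkers". Seven follow: WBC count, HDL-C, 8-epi-prostaglandin F2α, 11-dehydrothromboxane B2, sICAM-1, total NNAL and COHb. They have no order, no split of the significance level and no success rule.
- Section 6.3.1 compares each test arm with control "in the mean absolute change from Baseline to Week 24 (Visit 5) in each primary biomarker". The model code takes one response at a time.
- The only multiplicity step is in the same section: "Pairwise comparisons (Test 1 vs. control, and Test 2 vs. control) will be performed", and this is done "using a Dunnett's test at a 2-sided significance level of 0.05 to adjust for multiplicity".
- Section 4: "The mITT and PP populations will be used for the analyses of the primary endpoint". Section 6.3.1 repeats this: "The analysis will be conducted on the mITT and PP datasets". Neither place says which set decides. Section 4 also says that "The PP population will be a subset of the mITT Population".
- The Section 10 shells print a comparison p-value for both sets: tables 14.2.1.X.4.2 for mITT and 14.2.1.X.5.2 for PP.
- Section 3 describes the analysis of this smaller extension as largely exploratory.

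**The concern.** A Dunnett test over two arms holds the error at 5% for one biomarker. With seven biomarkers all labelled primary, the plan gives seven separate 5% chances of a false claim and no rule for reading them together.

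The gap matters most for the five biomarkers of potential harm (WBC, HDL-C, the two urinary eicosanoids and sICAM-1). I assume that total NNAL and COHb, the two exposure markers, do fall in smokers who stop. The open question is then whether anything moves among the other five. Under the present wording, one p-value below 0.05 among them can be reported as a multiplicity-adjusted primary result, although no allowance was made for the search over biomarkers. The absence of a named lead set adds a second choice.

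**Working it through.** **Inputs.** From the SAP: 7 primary biomarkers; two-sided 0.05; 2 test-vs-control comparisons per biomarker; arms of 50 (Test 1), 48 (Test 2) and 52 (Control) from section 3; PP nested in mITT. Not in the SAP, so assumed: the correlation between biomarkers and the share of mITT that stays in PP. The Dunnett step is taken as the two-comparison test in the text of 6.3.1.

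**Step 1: the plan's own 5%.** Correlation of the two contrasts = sqrt[(50/102) × (48/100)] = 0.485. In the normal approximation, the two-sided Dunnett critical value at 0.05 is 2.21 (0.0268 per comparison). Simulation under the null gives 5.0-5.1% for one biomarker in one set. The stated level is reproduced.

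**Step 2: across biomarkers, one set, all nulls true.**
- Independent, seven: 1 − 0.95^7 = 0.302.
- Independent, five: 1 − 0.95^5 = 0.226.
- Equally correlated biomarkers, simulated with the actual arm sizes:

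| Assumed correlation | Seven biomarkers | Five harm biomarkers |
|---|---|---|
| 0.2 | 29% | 22% |
| 0.4 | 26% | 20% |
| 0.6 | 21% | 17% |

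Even at correlation 0.8, seven biomarkers give about 15%.

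**Step 3: a hit in either set counts.** Here PP is taken as a random 90%, 70% or 50% of mITT. Seven biomarkers:

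| Assumed correlation | PP 90% | PP 70% | PP 50% |
|---|---|---|---|
| 0 | 37.5% | 42.9% | 45.6% |
| 0.5 | 29.6% | 33.8% | 36.5% |
| 0.8 | 19.5% | 22.5% | 24.4% |

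For one biomarker the second set lifts the error from 5% to 6.5-8.5%. Most of the excess comes from the seven biomarkers.

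**Step 4: which cross-biomarker rule works.** There are 7 × 2 = 14 test-vs-control p-values at Week 24, so a Holm step across seven biomarkers must say what enters it. I simulated independent biomarkers, with a Test 1 effect of 1 SD on none, two, four or all seven biomarkers and Test 2 inert:
- Holm on each biomarker's smaller Dunnett-adjusted p-value, with claims about the biomarker only: at most 4.9%.
- The same ordering, but with both arms read at each step: 4.9%, 5.6%, 6.7% and 7.6%. This does not hold 5%.
- Holm over the 14 unadjusted p-values, with arm-specific claims: 4.7% throughout.

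**Step 5: price of the rule.** If NNAL and COHb are rejected first, the next Holm level is 0.05/5 = 0.01, with Dunnett critical value 2.80. The effect detectable with 80% power for Test 1 vs Control is (critical value + 0.84) × sqrt(1/50 + 1/52), where the square root is 0.198:
- At 0.05: (2.21 + 0.84) × 0.198 ≈ 0.61 SD.
- At 0.01: (2.80 + 0.84) × 0.198 ≈ 0.72 SD.

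The 14-value rule costs about the same. With four p-values rejected, the next level is 0.05/10 = 0.005, critical value 2.81, again about 0.72 SD.

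**The case against.** The best defence is that the plan never promises control across biomarkers. The sentence that invokes Dunnett names the two arm comparisons it covers. Section 2.2 presents each biomarker as its own outcome with no at-least-one criterion, and section 3 calls the work largely exploratory. If each biomarker is read separately, familywise control is a design choice.

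Much of this stands. A reader might infer that the SAP misstates what Dunnett does; it does not. A reader might also infer that some false-positive primary result is likely. The figures do not support that: every scenario is below one half, and a true difference in some biomarkers lowers the risk further. Nor do the 28 p-values (7 × 2 arms × 2 sets) act as 28 separate chances. The arms share a control group, Dunnett handles each pair, and PP is part of mITT.

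It is also fair that the two sets are not treated alike elsewhere. The secondary biomarker comparisons (6.3.2), the subgroups (6.3.4) and the carried-forward analysis (6.3.5.2) use mITT. But the primary objective in 2.1.1 is about smokers who have switched fully, defined by exclusive use, exhaled CO and NNN. The PP criteria in section 4 follow that definition more closely than mITT does. The SAP leans both ways and does not settle it.

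What the defence does not remove is the combination of a primary label, a 0.05 significance level and an unqualified reference to multiplicity adjustment. The remark in section 3 covers most of the analysis without saying which part is not exploratory.

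**Conclusion.** The point holds as a gap in error control. Across the seven primary biomarkers the error is uncontrolled: under the global null it is 30% in one set if they are independent and about 21-29% at correlations of 0.6-0.2. For the five harm biomarkers alone it is about 17-23%. Counting a hit in either set raises it, to 46% in the most extreme case tried.

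The 30% and 23% follow from the SAP's own level once independence is assumed. The other figures rest on assumed equal correlations and, for the two-set case, on PP being a random part of mITT. PP is in fact selected on compliance, so the two-set figures are only a guide. The seven-biomarker figures are a worst case if NNAL and COHb truly change; the five-biomarker figures are then the relevant ones.

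**What to change.** 1. State in 6.3.1 which set carries the Week 24 primary conclusion, after reconciling the choice with the full-switching objective in 2.1.1. Make the other set supportive.
2. Keep all per-biomarker Dunnett results as planned.
3. Add one column to that set's Week 24 comparison tables (14.2.1.X.4.2 if mITT, 14.2.1.X.5.2 if PP). For biomarker-level claims, it applies Holm across the seven biomarkers to each one's smaller Dunnett-adjusted p-value. For arm-specific claims, it applies Holm across the 14 unadjusted Week 24 test-vs-control p-values. Fix in advance which kind of claim is intended.
4. State that any claim of a primary biomarker effect across the panel rests on that column, and that the Dunnett p-values are not adjusted across biomarkers.

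The cost is SAP wording and one table column, with no new data and no planned result dropped. The downside is that a borderline harm-biomarker result may no longer be called significant, by the margin shown in step 5 of the working.
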